7.8 Pharmacokinetics

Not applicable.

7.9 Pharmacogenetics/pharmacogenomics

Not applicable.

7.10 Other biomarkers

Not applicable.

8 Safety monitoring

8.1 Adverse Events (AEs)/Serious Adverse Events (SAEs)

An adverse event is the appearance or worsening of any undesirable sign, symptom, or medical condition occurring after first drug intake even if the event is not considered to be related to drug therapy. Medical conditions/diseases present before obtaining informed consent are only considered adverse events if they worsen after starting trial. Abnormal laboratory values or test results constitute adverse events only if they induce clinical signs or symptoms, are considered clinically significant, require medication discontinuation or require therapy.

The occurrence of adverse events should be sought by non-directive questioning of the patient at each visit during the trial. Adverse events also may be detected when they are volunteered by the patient during or between visits or through physical examination, laboratory test, or

other assessments. All adverse events must be recorded on the Adverse Events CRF with the following information:

1. its relationship to Fingolimod (suspected/not suspected)
2. its duration (start and end dates or if continuing at final exam)
3. whether it constitutes a serious adverse event (SAE)

An SAE is defined as an event which:

- is fatal or life-threatening
- results in persistent or significant disability/incapacity
- constitutes a congenital anomaly/birth defect
- requires inpatient hospitalization or prolongation of existing hospitalization, unless hospitalization is for:
 - routine treatment or monitoring of the studied indication, not associated with any deterioration in condition (e.g. hospitalization for relapse treatment)
 - elective or pre-planned treatment for a pre-existing condition that is unrelated to the indication under study and has not worsened since the start of study drug
 - treatment on an emergency outpatient basis for an event not fulfilling any of the definitions of a SAE given above and not resulting in hospital admission
 - social reasons and respite care in the absence of any deterioration in the patient's general condition
- is medically significant, i.e., defined as an event that jeopardizes the patient or may require medical or surgical intervention to prevent one of the outcomes listed above

Unlike routine safety assessments, SAEs are monitored continuously and have special reporting requirements; see Section 8.2.

Information about adverse reactions observed in relation to fingolimod can be found in the local product labeling.

All adverse events should be treated appropriately. Treatment may include one or more of the following: no action taken (i.e., further observation only); medication temporarily interrupted; medication permanently discontinued due to this adverse event; concomitant medication given; non-drug therapy given; patient hospitalized/patient's hospitalization prolonged. The action taken to treat the adverse event should be recorded on the Adverse Event CRF.

Once an adverse event is detected, it should be followed until its resolution or until it is judged to be permanent, and assessment should be made at each visit (or more frequently, if necessary) of any changes in severity, the suspected relationship to the medication, the interventions required to treat it, and the outcome.

Information about side effects already known about the investigational drug can be found in the Investigator's Brochure (IB) or will be communicated between IB updates in the form of SUSAR reports for the investigator and if applicable in the form of Investigator Notifications. This information will be included in the patient informed consent and should be discussed with the patient during the study as needed.

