7.7 MS Relapse

A patient should report symptoms indicative of an MS relapse at a scheduled visit or any other time. Patients must be instructed to immediately contact the study site if he/she develops new, reoccurring or worsening neurological symptoms. Standard therapy with corticosteroids can be used. Following an onset of MS relapse the patient may have unscheduled visits at the discretion of the investigator. Handling of MS relapses will be performed according to local practice and standard of care procedures. Details of MS relapse handling will be recorded in the corresponding CRF.

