Although disease progression of multiple sclerosis, including MS relapses, may be classified as medically significant, is often requiring hospitalization or results in a newly acquired disability / invalidity and therefore the criteria for an SAE can be met, these adverse events should only be documented in the source data and the CRF, respectively.

In case of a heavy or unexpected event (e.g. death) according to the investigators judgment a single case report may be required. The SAE form should then be filled as usual and the SAE reported to the company.

The responsible physician must verify all information given in the questionnaires of the patients for the presence of an adverse event and report this in the CRF respectively

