2.8.1 Adverse events (AEs)

Adverse events which started before BL/M0 were listed only. Analyses were performed on AEs which started at/after BL/M0.

The incidence of adverse events is displayed with n, percentage and 95% confidence interval for the SAF. Here, different types of AEs are presented:

- (1) Any AE
- (2) AE with suspected relationship to fingolimod
- (3) AE leading to study drug dosage adjustment/temporary interruption
- (4) AE leading to permanent study drug discontinuation
- (5) Serious adverse event
- (6) Non-Serious AE
- (7) Death

For AEs of type (1) to (6) a two-level frequency table for MedDRA system organ classes (SOC) and Preferred Terms (PT) within SOC are presented. Here, a patient with multiple occurrences is counted only once on the respective class.

The maximum severity of (several) AEs occurring in a patient ist displayed for PTs within SOC, SOC and overall.

For AEs of type (7), (5), and (3) separate listings are generated.

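### Protocol 8.1 and 8.2 leave the seriousness flag for a hospitalised MS relapse open to opposite readings, and the overall AE percentages in SAP 2.8.1 inherit that

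*Protocol*

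**What the plan says.** **Definition (Protocol 8.1).** A hospital stay does not make an event serious if it is for "routine treatment or monitoring of the studied indication, not associated with any deterioration in condition (e.g. hospitalization for relapse treatment". This carve-out belongs to the hospitalisation criterion alone. The criterion for an event that "results in persistent or significant disability/incapacity" has no relapse exception, and neither does the medically significant criterion. Every adverse event goes on the Adverse Events CRF, with a record of "whether it constitutes a serious adverse event (SAE").

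**Exception for relapse (Protocol 8.2).** Progression or relapse "is often requiring hospitalization or results in a newly acquired disability / invalidity and therefore the criteria for an SAE can be met". The instruction that follows is that "these adverse events should only be documented in the source data and the CRF, respectively". No CRF page is named, and nothing is said about the seriousness flag. Severe or unexpected cases may return to SAE reporting if the investigator judges so.

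**Relapse (Protocol 7.7).** Relapse shows itself as new, recurring or worsening neurological symptoms. "Details of MS relapse handling will be recorded in the corresponding CRF". The section does not say how that entry relates to the AE CRF.

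**Analysis (SAP 1.2, 2.8.1, 2.8.1.1).** Incidence of AEs and SAEs is a secondary endpoint in the Safety Set. SAP 2.8.1 reports n, percentage and 95% confidence interval for seven types, among them any AE, SAE and non-serious AE. It neither includes nor excludes relapse, and does not say whether SAEs come from the AE CRF flag or the SAE report form. SAP 2.8.1.1 defines no grouping of AEs.

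**The concern.** The cohort has relapsing MS and is followed for 36 months, so some relapses are to be expected, and some may lead to a hospital stay. Protocol 6.6.3 allows steroid treatment as an inpatient or outpatient and leaves relapse handling to local practice, at about 11 sites. Whether a relapse leads to admission can therefore differ by site. If the seriousness flag can differ as well, the overall SAE percentage partly measures how sites read the protocol. It also mixes activity of the disease under study with the safety of the drug. The printed confidence interval covers sampling error only and gives no sign of this.

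**Working it through.** **Step 1: the readings side by side.** Take one relapse treated in hospital and ask how a site sets the flag on the AE CRF.

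| Text followed | Reasoning | Flag |
|---|---|---|
| 8.1, the example | Relapse hospitalisation is named as exempt | Not serious through hospitalisation |
| 8.1, the condition | Exemption needs no deterioration; a relapse is new or worsening symptoms (7.7) | Serious |
| 8.1, other criteria | Disability or medical significance, no relapse exception | Serious if met |
| 8.2 | Hospitalisation and disability named as reasons the SAE criteria can be met; only the report is waived | Can be serious, without an SAE form |

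Both values of the flag are defensible from the text.

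**Step 2: which rows move.** The flag shifts the event between the SAE and non-serious AE rows. The any-AE row does not depend on the flag. It depends only on whether the relapse is entered on the AE CRF at all.

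**Step 3: size.** The plan states no SAE rate or relapse rate, so there is no figure to reproduce. Let N be the size of the Safety Set and k the number of patients whose only SAE is a relapse flagged serious. Then

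shift in SAE incidence = 100 × k / N percentage points.

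With N = 100 (the planned enrolment, Protocol 10.7), this is k points, or one point per such patient.

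**Step 4: illustration.** Assumed, not in the documents: 5 or 10 patients per 100 with another SAE, 5 to 20 per 100 with a hospitalised relapse, and no overlap. Intervals are exact (Clopper-Pearson) 95%.

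| Other SAE | Hospitalised relapse | None flagged serious | All flagged serious |
|---|---|---|---|
| 10 | 5 | 10% (4.9 to 17.6) | 15% (8.6 to 23.5) |
| 10 | 10 | 10% (4.9 to 17.6) | 20% (12.7 to 29.2) |
| 10 | 20 | 10% (4.9 to 17.6) | 30% (21.2 to 40.0) |
| 5 | 10 | 5% (1.6 to 11.3) | 15% (8.6 to 23.5) |

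Inconsistency between sites falls between the two columns. In the second row, with half of the relapses flagged, the result is 15% (8.6 to 23.5). With 5 relapse patients, the all-flagged value of 15% still lies inside the none-flagged interval. With 10, the value of 20% lies above that interval's upper limit of 17.6%.

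**The case against.** **The two sections agree on SAE reporting.** Both keep an ordinary hospitalised relapse off the SAE report form, so a reader who infers a conflict over expedited reporting goes too far. This stands. If SAEs were counted only from SAE forms, the effect on the SAE row would shrink to the cases left to investigator judgment. The SAP does not say that they are.

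**A relapse does reach the AE CRF.** One might infer from 7.7 that a relapse could end up only on a separate relapse form. The text gives that little support: 8.1 puts all adverse events on the AE CRF, 8.2 calls relapses adverse events, and 7.7 neither describes a separate form nor says that its entry replaces the AE entry. The any-AE row is therefore exposed only if a site misreads 7.7.

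**Relapses would be visible.** SAP 2.8.1 tabulates preferred terms for all types except death and lists SAEs separately, so relapses coded as AEs would show. This stands against any claim that they are hidden. It does not correct the overall SAE percentage or its interval when sites set the flag differently.

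**The effect might be thought large.** A reader could assume 0.1 to 0.3 relapses per patient-year, so that 1 − exp(−3r) gives 26% to 59% of patients with a relapse in 3 years. Multiplying by an assumed hospitalised share of 10% to 40% gives about 3 to 24 points. The documents supply neither input. The product also assumes full follow-up, no overlap with other SAEs and a switch from no hospitalised relapse flagged to all of them, and applies the share per patient rather than per relapse. It should not be quoted as the size.

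**Conclusion.** The point holds as a defect of classification in a secondary safety endpoint. The protocol text supports both values of the seriousness flag for the same hospitalised relapse, and the SAP has no rule that makes the overall rows independent of the choice. The size cannot be known from the documents. It is one percentage point of SAE incidence per 100 patients for each patient whose only SAE is a relapse, provided that SAEs are counted from the AE CRF flag.

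A reader might call this a threat to the study's headline result. It is not: the study has one arm, the SAP tests no hypothesis, and the primary endpoint, change in RNFLT, does not use these data. The point still deserves correction before database lock, because the safety percentages will be read as properties of the drug and the remedy is cheap.

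**What to change.** 1. **Protocol.** Reconcile 8.1, 8.2 and 7.7 so that they state one rule on which CRF page takes a relapse and how its seriousness flag is set. Which rule to adopt is for the sponsor to decide.
2. **SAP 2.8.1, source.** State whether SAEs are counted from the AE CRF flag or from the SAE report form.
3. **SAP 2.8.1, tables.** Show the overall any-AE, SAE and non-serious AE rows both with and without the preferred terms for MS relapse and progression, listing those terms before database lock. The rows without them do not depend on how sites flagged relapse. Which set comes first is the sponsor's choice.
4. **Relapses.** Summarise them in a row of their own.

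**Cost.** The SAP changes need a term filter and a few more table rows, with no recoding of collected data. The protocol change is an amendment, and Appendix 1 requires approval by the sponsor, the Health Authority and the ethics committee. It would not by itself change flags already recorded. If it comes too late to be useful, items 2 to 4 can still be done.

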8.1.1 Reporting of ambulatory ECG (Holter-ECG)-related adverse device events

An adverse device event is any malfunction or deterioration in the characteristics and/or performance of a device, as well as any inadequacy in the labeling or the instructions for use which, directly or indirectly, might lead to or might have led to the death of a patient/subject, or user or of other persons or to a serious deterioration in their state of health.

For the purposes of compliance with the Medical Device Directive (MDD), adverse device events must be documented on the Adverse Device Event Report Form and submitted to the manufacturer of the ambulatory ECG (Holter-ECG) equipment used via fax or email within 24 hours of learning of the event. The contact details for reporting of ambulatory ECG (Holter-ECG)-related adverse device events are provided in the investigator folder provided to each site. The original copy of the Adverse Device Event Report Form and the confirmation of the submission must be kept in the study participant's file at the site.

Should an adverse event or Serious Adverse Event be connected to a device-related complication, the complication has to be documented and reported 1. to Novartis as AE /SAE via AE record and/or SAE report as well as 2. to the ECG manufacturer using the Adverse Device Event Report Form.

8.2 Serious adverse event reporting

To ensure patient safety, every SAE, regardless of suspected causality to a pharmaceutical product or procedure occurring in a study participant after the patient has provided informed consent and until 8 weeks after the patient has stopped study participation (defined as time last visit) must be reported to Novartis within 24 hours of learning of its occurrence.

Any SAEs experienced after this 8-week period should only be reported to Novartis if the investigator suspects a causal relationship to fingolimod.

Recurrent episodes, complications, or progression of the initial SAE must be reported as follow-up to the original episode, regardless of when the event occurs. This report must be submitted within 24 hours of the investigator receiving the follow-up information. An SAE that is considered completely unrelated to a previously reported one should be reported separately as a new event.

Information about all SAEs is collected and recorded on the Serious Adverse Event Report Form. The investigator must assess the relationship to fingolimod, complete the SAE Report Form in English, and send the completed, signed form by fax within 24 hours to the local Novartis Drug Safety & Epidemiology Department. The telephone and telefax number of the contact persons in the local department of Drug Safety & Epidemiology, are listed in the investigator folder provided to each site. The original copy of the SAE Report Form and the fax confirmation sheet must be kept with the case report form documentation at the study site.

Follow-up information is sent to the same person to whom the original SAE Report Form was sent, using a new SAE Report Form stating that this is a follow-up to the previously reported SAE and giving the date of the original report. The follow-up information should describe whether the event has resolved or continues, if and how it was treated, and whether the patient continued or withdrew from study participation.

If the SAE is not previously documented in the Investigator's Brochure (new occurrence) and is thought to be related to the Novartis drug, a Drug Safety & Epidemiology Department associate may urgently require further information from the investigator for Health Authority reporting. Novartis may need to issue an Investigator Notification (IN) to inform all investigators involved in any study with the same drug that this SAE has been reported.

Exception: Progression of multiple sclerosis / MS relapse

Although disease progression of multiple sclerosis, including MS relapses, may be classified as medically significant, is often requiring hospitalization or results in a newly acquired disability / invalidity and therefore the criteria for an SAE can be met, these adverse events should only be documented in the source data and the CRF, respectively.

In case of a heavy or unexpected event (e.g. death) according to the investigators judgment a single case report may be required. The SAE form should then be filled as usual and the SAE reported to the company.

The responsible physician must verify all information given in the questionnaires of the patients for the presence of an adverse event and report this in the CRF respectively

8.3 Pregnancies

Pregnancies are not allowed by the study protocol and women of child bearing potential should be excluded from participation in the study unless they use effective contraception as described in 7.5.4. Any pregnancy that occurs during study participation should be reported by the investigator to the local Novartis Drug Safety & Epidemiology Department using a Clinical Trial Pregnancy Form for up to 2 months following the last visit.

Patients becoming pregnant while on FTY720 should be withdrawn from the study. To ensure patient safety each pregnancy must also be reported to Novartis within 24 hours of learning of its occurrence. The pregnancy should be followed up to determine outcome, including spontaneous or voluntary termination, details of birth, and the presence or absence of any birth defects, congenital abnormalities or maternal and newborn complications. Pregnancy follow-up should be recorded on the same form and should include an assessment of the possible relationship to the Novartis drug of any pregnancy outcome. Any SAE experienced during pregnancy must be reported on the SAE Report Form.

It is recommended that pregnant study participants, administered fingolimod, are registered (if they consent) in the fingolimod pregnancy registry.

8.4 Data Monitoring Board

Not applicable.

9 Data review and database management

9.1 Site monitoring

Before study initiation, at a site initiation visit or at an investigator's meeting, a Novartis representative will review the protocol and CRFs with the investigators and their staff. During the study, the field monitor will visit the site regularly to check the completeness of patient records, the accuracy of entries on the CRFs, the adherence to the protocol and to Good Clinical Practice, and the progress of enrollment. Key study personnel must be available to assist the field monitor during these visits.

The investigator must maintain source documents for each patient in the study, consisting of case and visit notes (hospital or clinic medical records) containing demographic and medical information, laboratory data, electrocardiograms, and the results of any other tests or assessments. All information on CRFs must be traceable to these source documents in the patient's file. The investigator must also keep the original informed consent form signed by the patient (a signed copy is given to the patient).

The investigator must give the monitor access to all relevant source documents to confirm their consistency with the CRF entries. Novartis monitoring standards require full verification for the presence of informed consent, adherence to the inclusion/exclusion criteria, documentation of SAEs, and the recording of data that will be used for all primary and safety variables. Additional checks of the consistency of the source data with the CRFs are

performed according to the study-specific monitoring plan. No information in source documents about the identity of the patients will be disclosed.

9.2 Data collection

Designated investigator staff must enter the information required by the protocol onto the Novartis CRFs that are printed on 3-part, non-carbon-required paper. Field monitors will review the CRFs for completeness and accuracy and instruct site personnel to make any required corrections or additions. The CRFs are forwarded to Data Management by field monitors, one copy being retained at the investigational site. Once the CRFs are received by Data Management, their receipt is recorded and they are reviewed prior to data entry.

9.3 Database management and quality control

Data from the CRFs are entered into the study database by Contract Research Organization staff following their own internal standard operating procedures that have been reviewed and approved by Novartis.

Subsequently, the entered data are systematically checked by Data Management staff, using error messages printed from validation programs and database listings. Obvious errors are corrected by Data Management personnel preliminarily. However, a listing with these performed obvious corrections will be sent to the respective investigators for approval. Other errors or omissions are entered on Data Query Forms, which are returned to the investigational site for resolution. The signed original and resolved Data Query Forms are kept with the CRFs at the investigator site, and a copy is sent to Novartis so the resolutions can be entered into the database. Quality control audits of all key safety and efficacy data in the database are made prior to locking the database.

Concomitant medications entered into the database will be coded using the WHO Drug Reference List, which employs the Anatomical Therapeutic Chemical classification system. Medical history/current medical conditions and adverse events will be coded using the Medical dictionary for regulatory activities (MedDRA) terminology.

OCT assessments (including last OCT measurement prior to first intake of fingolimod, if available) are evaluated and quality controlled centrally by Dr. [REDACTED], data will be recorded and stored at [REDACTED].

Laboratory samples will be processed locally.

At the conclusion of the study, the occurrence of any protocol violations will be determined. After these actions have been completed and the database has been declared to be complete and accurate, it will be locked and made available for data analysis. Any changes to the database after that time can only be made by joint written agreement between the Trial Statistician and Statistical Reporting and the Clinical Trial Leader.

10 Data analysis

